### **8.5.4 Clinical Laboratory Findings**

Clinical laboratory variables will be presented in two ways. First, the mean change from baseline to each scheduled visit will be summarized. Second, the number and percent of participants with treatment-emergent PCS laboratory values will be tabulated. Treatment-emergent PCS laboratory tests are those in which the baseline value is normal and post-baseline value is abnormal (i.e., meets Grade III or Grade IV toxicity criteria from the NCI-CTC Version 5 or higher). Baseline will be defined as the last value obtained before randomization.

No formal statistical tests will be performed.

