## 2.3 DEFINITIONS AND CONVENTIONS FOR DATA HANDLING

### 2.3.1 Baseline Definition

For evaluations collected at multiple time points, the baseline will be defined as the last value obtained before randomization.

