### **7. SAFETY ANALYSES**

All safety analyses will be performed on the Safety Population. Safety assessments include:

- Extent of exposure
- Adverse events
- Laboratory assessments (hematology, iron indices, chemistry, and other)

- Vital signs

Baseline of clinical laboratory findings will be defined as the last value obtained before randomization.

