### **7.3 CLINICAL LABORATORY PARAMETERS**

Laboratory assessments include hematology, clinical chemistry, and iron indices:

- Hematology: Hgb, Hct, RBC, WBC, MCV, MCH, MCHC, RDW, platelets, differential count, reticulocyte count and reticulocyte hemoglobin content (CHr)
- Clinical chemistry: sodium, potassium, chloride, BUN, creatinine, albumin, alkaline phosphatase, total bilirubin, GGT, AST, ALT, LDH, calcium, phosphorus, glucose, bicarbonate and magnesium.
- Iron indices: serum iron, serum ferritin, and total iron binding capacity (TIBC), and percentage serum transferrin saturation (TSAT).
- Other: Serum pregnancy test

All laboratory parameters will be presented in conventional units. The actual value and mean change from baseline to each scheduled visit will be summarized using descriptive statistics by treatment for each laboratory test group above. All abnormal laboratory values will be presented in listings.

Time course table for serum phosphate will be constructed for FCM subjects in safety population. Descriptive statistics of days to first value of specified CTC grade and days to return to normal will be summarized. Only the subjects that were under FCM treatment and had a normal serum phosphate baseline value will be included in this table.

The number and percent of subjects with treatment-emergent potentially clinically significant (PCS) laboratory values after baseline will be summarized by visit and by treatment. The denominator is all subjects with normal baseline and at least one post baseline assessment in the

safety population and the numerator is the number of subjects with PCS (i.e., meets Grade 3 or Grade 4 AE scale defined in Division of AIDS (DAIDS) Table for Grading the Severity of Adult and Pediatric Adverse Events, Version 2.1 from March 2017 (Division of AIDS, National Institute of Allergy and Infectious Diseases, National Institutes of Health, US Department of Health and Human Services)) at any post-baseline visit.

Shift from baseline AE grade to maximum post-baseline AE grade, and shift from baseline to the last visit in terms of AE grade will be summarized by treatment, separately.

The AE grade for Chemistries and Hematology are defined in Appendix 1.1. BUN, hematocrit, bands and iron indices do not have adverse event scales available and are not evaluated separately as possible AEs.

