**10. APPENDICES**

**APPENDIX 1.1 ADVERSE EVENT SCALE**

CHEMISTRIES Adverse Event Scale				
PARAMETER	GRADE 1 MILD	GRADE 2 MODERATE	GRADE 3 SEVERE	GRADE 4 POTENTIALLY LIFE- THREATENING
Albumin, Low (g/dL; g/L)	3.0 to < LLN 30 to < LLN	≥ 2.0 to < 3.0 ≥ 20 to < 30	< 2.0 < 20	NA
Alkaline Phosphatase, High	1.25 to < 2.5 x ULN	2.5 to < 5.0 x ULN	5.0 to < 10.0 x ULN	≥ 10.0 x ULN
ALT or SGPT, High Report only one	1.25 to < 2.5 x ULN	2.5 to < 5.0 x ULN	5.0 to < 10.0 x ULN	≥ 10.0 x ULN
AST or SGOT, High Report only one	1.25 to < 2.5 x ULN	2.5 to < 5.0 x ULN	5.0 to < 10.0 x ULN	≥ 10.0 x ULN
Calcium, High (mg/dL; mmol/L) ≥ 7 days of age	10.6 to < 11.5 2.65 to < 2.88	11.5 to < 12.5 2.88 to < 3.13	12.5 to < 13.5 3.13 to < 3.38	≥ 13.5 ≥ 3.38
Calcium, Low (mg/dL; mmol/L) ≥ 7 days of age	7.8 to < 8.4 1.95 to < 2.10	7.0 to < 7.8 1.75 to < 1.95	6.1 to < 7.0 1.53 to < 1.75	< 6.1 < 1.53
Creatinine, High Report only one	1.1 to 1.3 x ULN	> 1.3 to 1.8 x ULN OR Increase to 1.3 to < 1.5 x participant's baseline	> 1.8 to < 3.5 x ULN OR Increase to 1.5 to < 2.0 x participant's baseline	≥ 3.5 x ULN OR Increase of ≥ 2.0 x participant's baseline
Potassium, High (mEq/L; mmol/L)	5.6 to < 6.0 5.6 to < 6.0	6.0 to < 6.5 6.0 to < 6.5	6.5 to < 7.0 6.5 to < 7.0	≥ 7.0 ≥ 7.0
Potassium, Low (mEq/L; mmol/L)	3.0 to < 3.4 3.0 to < 3.4	2.5 to < 3.0 2.5 to < 3.0	2.0 to < 2.5 2.0 to < 2.5	< 2.0 < 2.0
Sodium, High (mEq/L; mmol/L)	146 to < 150 146 to < 150	150 to < 154 150 to < 154	154 to < 160 154 to < 160	≥ 160 ≥ 160
Sodium, Low (mEq/L; mmol/L)	130 to < 135 130 to < 135	125 to < 130 125 to < 130	121 to < 125 121 to < 125	≤ 120 ≤ 120

ULN and LLN required for the chemistries AE Scale (based on the high and low range from Covance Central Laboratory Services Manual, American Regent, Inc)								
Sex	Age	Alkaline Phosphatase LLN (U/L)	ALT ULN (U/L)	AST ULN (U/L)	Age	Creatinine ULN (mg/dL)	Age	Albumin LLN (g/dL)
Female	1-4 yr	<108	>34	>56	1-4 yr	>0.4	2 m-4 yr	<2.8
	4-7 yr	<96	>34	>48	4-7 yr	>0.5	4-16 yr	<2.9
	7-10 yr	<69	>34	>40	7-10 yr	>0.6	16-18 yr	<3.3
	10-15 yr	<51	>34	>40	10-13 yr	>0.7	18 yr	<3.3
	15-18 yr	<31	>34	>40	13-16 yr	>0.8		

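### Three SAP laboratory-safety rules are wrong as printed: the alkaline phosphatase limits, albumin Grades 1 and 2 below age 16, and pre-dose Day 0 values that count as treatment-emergent

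*SAP*

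**What the plan says.** **Grading.** SAP 7.3 states that "The AE grade for Chemistries and Hematology are defined in Appendix 1.1". Appendix 1.1 has a row "Alkaline Phosphatase, High" whose four grades are all multiples of the ULN. A second table, introduced as "ULN and LLN required for the chemistries AE Scale" and sourced to the central laboratory manual, supplies the limits. Its alkaline phosphatase column has a heading that begins "Alkaline Phosphatase LLN (U/L". For albumin, Grade 1 runs from 3.0 g/dL up to the LLN, Grade 2 from 2.0 to below 3.0 g/dL, and Grade 3 is below 2.0 g/dL.

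**Baseline.** Three places agree. Protocol 8.5.4: "Baseline will be defined as the last value obtained before randomization". SAP 2.3.1: "the baseline will be defined as the last value obtained before randomization". SAP 7: "Baseline of clinical laboratory findings will be defined as the last value obtained before randomization".

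**Use.** SAP 7.3 counts a participant as PCS if a normal baseline is followed by a Grade 3 or 4 value at any visit after baseline. It also tabulates PCS by visit, and shifts from baseline grade to the worst later grade and to the last visit. A phosphate time-course table covers FCM participants with a normal baseline phosphate. Protocol 8.5.4 adds that "No formal statistical tests will be performed".

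**The concern.** The appendix is the specification from which the grades will be programmed. If a limit is missing, the programmer must go outside the SAP for it. If two bands conflict with the printed limits, normal results are displayed as moderate abnormalities.

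The baseline rule raises a different problem. The label treatment-emergent should mean that the abnormality appeared after treatment began. Here the dividing line is randomization, and a scheduled blood draw lies between randomization and the first dose. Safety is part of the primary objective of this pediatric trial, so laboratory tables that misattribute or misgrade values matter even though nothing is tested on them.

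**Working it through.** The plan gives no figure to reproduce on this point. The check puts the printed limits into the printed bands and sets the order of Day 0 procedures against the baseline rule.

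**1. Alkaline phosphatase.** Inputs: the grade row and limits table of SAP Appendix 1.1.

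- Needed: a ULN, since Grade 1 starts at 1.25 × ULN, Grade 2 at 2.5 × ULN, Grade 3 at 5 × ULN and Grade 4 at 10 × ULN.
- Supplied (U/L), for ages 1-4, 4-7, 7-10, 10-15 and 15-18: girls 108, 96, 69, 51, 31; boys 104, 93, 86, 95, 50. All are LLNs.
- Every entry carries a less-than sign, while the ALT, AST and creatinine columns are headed ULN and carry greater-than signs. Heading and signs agree throughout, so this does not look like a text-extraction fault.
- Result: 0 of 10 bands give a ULN, so none of the four grades can be computed from the appendix. Grades 3 and 4 feed PCS, so both the PCS and shift tables depend on the missing limit.

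**2. Albumin.** Inputs: the albumin row and LLN column of the same appendix; the LLNs are the same for both sexes. Grade 1 is the interval [3.0, LLN), which is empty when the LLN is 3.0 or less. Normal values graded 2 are [LLN, 3.0).

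| Age | LLN (g/dL) | Grade 1 | Normal but Grade 2 |
|---|---|---|---|
| 1 to <4 | 2.8 | [3.0, 2.8): empty | 2.8 to <3.0; width 3.0 − 2.8 = 0.2 |
| 4 to <16 | 2.9 | [3.0, 2.9): empty | 2.9 to <3.0; width 3.0 − 2.9 = 0.1 |
| 16-17 | 3.3 | 3.0 to <3.3 | none |

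Ages 1 to 15 are 15 of the 17 eligible years of age. PCS for albumin needs a value below 2.0 g/dL, so only the shift tables change.

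**3. Day 0.** Protocol 6.3.1 gives this order:

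- Before IRT is contacted: eligibility check, physical examination and medication review. No blood is drawn.
- After assignment and before study drug: central-laboratory blood in all participants.
- Then the first dose.

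The Schedule of Events has six laboratory visits (screening and Days 0, 7, 14, 28 and 35). Only screening precedes randomization, so under the stated rule screening is the baseline and Day 0 falls after baseline. Neither document ties PCS to the first dose. Three consequences follow for a participant with a normal screening value:

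- A pre-dose Day 0 value of Grade 3 or 4 meets the any-visit PCS definition.
- A pre-dose Day 0 grade can be the worst grade after baseline in the shift table.
- In the FCM group, a low pre-dose phosphate can be the first qualifying value in the time-course table. By SAP 2.3.2 its date is Study Day 1.

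**4. Phosphate scale.** The time-course table refers to a CTC grade that it does not name. SAP Section 9 item 4 replaces CTC with DAIDS for identifying abnormal laboratory values. The two statements do not agree.

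**The case against.** **Alkaline phosphatase.** The table cites its source, so a careful programmer would find the right limit. That stands. A reader might go further and infer that values will be over-graded because the LLN is used as if it were the ULN. The documents do not support this: the column is plainly labelled LLN, and nothing tells the analyst to substitute it. They also give no ratio of ULN to LLN from which such an error could be sized.

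**Albumin.** The row is titled as low albumin, so it can be read as excluding values at or above the LLN. That is the sensible intention, but the Grade 2 cell carries no such condition, while the Grade 1 cell does refer to the LLN. The affected range is narrow, and the number of children in it is unknown.

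**Day 0.** Neither document calls Day 0 post-baseline outright; the status follows from combining the definitions, though nothing excludes it. The by-visit PCS table would show Day 0 values separately, and the shift to the last visit would normally be unaffected. The any-visit count and the worst-grade shift would not separate them. The contrast with adverse events is only partial: AE assessment starts with the first dose in both groups (Protocol 6.3.1), but the TEAE definition works on dates, not times of day. Moving the baseline for all laboratory tables would also give hemoglobin, ferritin, TSAT and CHr one change from baseline in the safety tables and another in the efficacy tables. That last objection is sound and limits the fix.

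**Phosphate.** A reader might infer that low phosphate has no graded display across both arms, since Appendix 1.1 has no phosphate row. That goes too far. Phosphorus is in the chemistry panel and is not among the tests that SAP 7.3 lists as lacking a scale. PCS cites the DAIDS table directly for both arms, and hypophosphatemia is an adverse event of special interest.

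**Conclusion.** The three rules need correction. High alkaline phosphatase cannot be graded from the SAP in any of the 10 bands. Below age 16, albumin Grade 1 is empty and a 0.1 or 0.2 g/dL range of normal values is shown as Grade 2. Pre-dose Day 0 abnormalities can be labelled treatment-emergent in the any-visit PCS count, the worst-grade shift and the phosphate time course.

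The first two conclusions rest on the printed tables alone. The third assumes that sites follow the Day 0 order in Protocol 6.3.1.

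The consequences are confined to descriptive tables, and the efficacy result does not change. A reader might also infer a bias between arms, or a fixed share of PCS values that are pre-dose. Neither is supported. The Day 0 draw is the same in both arms, so the main effect is misattributed events rather than a systematic difference. The documents also give no rate at which a normal screening value becomes Grade 3 or 4 by Day 0, so no count can be derived.

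**What to change.** 1. **Appendix 1.1, alkaline phosphatase.** Replace the LLN column with the age- and sex-specific ULN from the central laboratory manual that the table cites.
2. **Appendix 1.1, albumin.** Grade albumin only when it is below the age-specific LLN, and state that Grade 1 does not apply below age 16. Grade 2 then becomes 2.0 to <2.8 g/dL at ages 1 to <4 and 2.0 to <2.9 g/dL at ages 4 to <16.
3. **PCS, shift and phosphate time-course tables only.** Use the last value before first dose as the reference, and count only values after first dose as treatment-emergent. Keep the pre-randomization baseline for change-from-baseline summaries, so that hemoglobin, ferritin, TSAT and CHr agree with the efficacy tables. Record this in SAP Section 9 as a change from Protocol 8.5.4.
4. **Minor accompanying edit.** Reconcile the unnamed CTC grade in the phosphate time-course table with Section 9 item 4, and state the grade used.

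**Cost.** SAP wording, one corrected column, one albumin rule, one Section 9 entry and small programming edits. No new data are needed, because chemistry is already drawn in both arms at every visit. Participants abnormal at the Day 0 pre-dose draw leave the normal-baseline denominator for that test, and those abnormal at screening but normal at Day 0 enter it. The laboratory section will then use two reference points, so each table needs a footnote saying which one applies.

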## **7.4 VITAL SIGNS AND PHYSICAL EXAMINATION FINDINGS**

### **7.4.1 Vital Signs**

Vital signs will be collected including sitting body temperature, blood pressure (BP) and heart rate. On study drug dosing days BP and heart rate will be collected pre-dosing, immediately (within 5 minutes) post, and 30 minutes post dosing, and body temperature will be collected on each dosing day. For the FCM group, the actual value and the change in vital signs (including sitting heart rate and blood pressure) from pre-infusion to each post-infusion time point will be summarized descriptively on each dosing day. Markedly abnormal values should be determined by PALS Guidelines, 2015 in Appendix 1.2. Children >15 years of age will use the criteria for 15 years old children.

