### **Study Drug**

#### **Administration**

**Group A (FCM)** will receive 2 doses (Day 0 and Day 7) of FCM at 15 mg/kg to a maximum single dose of 750 mg (whichever is smaller) up to a maximum total dose of 1500 mg. FCM will be administered as either an undiluted IV push at a rate of 100 mg (2 mL)/minute OR in no more than 250 mL of normal saline and infused over 15 minutes.

**Group B (Oral ferrous sulfate)** will receive an age-dependent formulation of oral ferrous sulfate daily for 28 days as follows: participants <12 years of age will receive 6 mg (elemental iron)/kg/day divided into 2 daily doses of an oral liquid formulation, either drops or elixir, and participants  $\geq 12$  will receive 2 daily doses of oral tablets. Infants and children (ages 1 to <4 years) will receive oral ferrous sulfate drops, while children (ages  $\geq 4$  to <12 years) will have the option to receive oral ferrous sulfate elixir or oral ferrous sulfate tablets. Adolescents (ages  $\geq 12$  to 17 years) will receive an oral ferrous sulfate tablet (65 mg of elemental iron/tablet/dose) twice a day (BID). The maximum daily dose for all participants is 130 mg of elemental iron.

**Patient  
Assessments**

All participants who provide informed consent/assent, meet inclusion criteria, and do not meet exclusion criteria will be randomized. Starting on Day 0 (the time of study drug dosing) through Day 35, all randomized participants will be subject to safety assessments including vital signs (including sitting heart rate and blood pressure), laboratory samples include hematology, chemistries and iron indices, and adverse event queries. Participants receiving oral iron treatment will be assessed for degree of compliance.

**Primary  
Endpoint:**

Change in hemoglobin from baseline to Day 35.

**Secondary  
Endpoints:**

Change in ferritin from baseline to Day 35  
Change in TSAT from baseline to Day 35  
Changes from baseline in hemoglobin, ferritin, TSAT, and reticulocyte hemoglobin content throughout the study.  
Pharmacokinetic assessments, including  $C_{max}$ ,  $T_{max}$ ,  $AUC_{0-time\ last}$  measured concentration,  $AUC_{0-infinity}$ ,  $T_{1/2}$ , MRT, Cl,  $V_D$ ,  $V_{Dc}$ ,  $V_{Dss}$ , and  $V_{Darea}$ .

**Study duration  
per participant:**

Approximately 6 weeks

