### 5.3 IV Medication Precautions

When administering FCM, the following precautions will be taken:

- The participant will be evaluated clinically prior to drug administration to assess the development of clinically-significant conditions.
- The vials will be visually inspected for particulate matter and discoloration before use. If noted, the vial will not be used, and the Investigator or his designee will notify the sponsor or sponsor's designee for replacement of the study drug, and for direction on the return of the unused vial.
- Heart rate and blood pressure will be assessed pre-, immediately (within 5 minutes) post, and 30 minutes post administration. Participants will be discharged from the site by the Investigator or his or her designee only if there are no significant signs or symptoms 30 minutes after the administration is completed.
- The participant will be monitored for at least 30 minutes for serious acute reactions as hypersensitivity or bioactive (labile) iron reactions to non-dextran IV iron products have rarely been reported. The reactions include: hypotension, loss of consciousness, bronchospasm with dyspnea, shortness of breath, and seizures.
  - In the event a serious acute reaction is seen, the site must have the capability to provide appropriate resuscitation measures. These may include IV NS, IV epinephrine, steroids, and/or antihistamines.

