- Administer FCM as a slow IV injection at the rate of approximately 2 mL /minute or in no more than 250 mL of normal saline and infused over 15 minutes.
- Document start and stop time of FCM administration and the total dose administered and if diluted.
- Post-administration evaluation to include measurement of sitting heart rate and blood pressure immediately (within 5 minutes) after and 30 minutes after FCM administration.
- Adverse event / serious adverse event assessment (starting at beginning of FCM injection).

Group B:

- Oral ferrous sulfate dispensing:
  - The first dose of ferrous sulfate will be administered before the end of the Day 0 visit.
  - Parents or guardians of participants will be responsible for the administration of twice daily dosing of oral ferrous sulfate. Participants that experience adverse events may continue with a dose-reduced regimen [3 mg/kg twice daily] of oral ferrous sulfate after a consult with the investigator. **(See Section 6.3.5 for oral iron dose reduction)**
  - Parents or guardians of participants will be dispensed oral iron on Days 0, 7, and 14. Used dispensing packs/blisters/syringes will be returned and are to include both the empty containers and any unused medication.
  - A record of compliance will be maintained for each participant and reviewed at each study visit. **(See Section 6.3.2 for compliance assessment)**.
  - If the participant took less than the amount of oral iron expected, document the reason(s) for missed doses and counsel the participant/parents/guardians about the importance of taking the study drug as prescribed.
- Adverse event assessment (starting once the participant takes the first in-clinic dose).

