### 6.3.2 Day 7 and Day 14 Visit

All participants will return to the clinic on Day 7 and 14. Prior to the administration of the study drug (if applicable), the participant will be evaluated clinically to assess for the development of clinically significant conditions that may contraindicate dosing.

- Vital signs (including sitting heart rate and blood pressure)
- Blood samples for central lab hematology, chemistries and iron indices (Group A participants will have an additional blood sample for PK prior to dosing).
- Concomitant medications assessment
- Adverse events assessment
- ESA and IBD stability (if applicable)

For Group A participants the following will be performed on **Day 7 only**:

- Blood samples for PK immediately (within 5 minutes) post-dose and 60 minutes post dose.
- Verify amount of single FCM dose (15mg/kg up to a maximum dose of 750 mg).
- Pre-administration evaluation to include measurement of heart rate, blood pressure, and body temperature.
- Administer FCM as a slow IV injection at the rate of approximately 2 mL /minute or in no more than 250 mL of normal saline and infused over 15 minutes.
- Document start and stop time of FCM administration and the total dose administered and if diluted.
- Post-administration, obtain sitting heart rate and blood pressure immediately (within 5 minutes) after and 30 minutes after FCM administration.

For Group B participants the following will be performed:

- Oral iron dispensing (**Day 7 and Day 14**).
- Compliance will be assessed according to the following:

For ferrous sulfate tablets:

- Used blister packs will be returned and are to include both the empty containers and any unused medication.
- The blister packs will be examined to assess compliance (the number taken divided by the number of pills expected to be taken). A record of compliance will be maintained for each participant and reviewed.
- If the participant took less than the number of tablets expected, document the reason(s) for missed doses and counsel the participant/parent/guardian about the importance of taking the study drug as prescribed.

For ferrous sulfate drops and elixir:

- Used oral syringes will be returned which will include any unused medication.

- The oral syringes will be examined to assess compliance (the volume remaining in the oral syringes divided by the expected amount to be taken). A record of compliance will be maintained for each participant and reviewed.

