## 7.2 ADVERSE EVENTS

Adverse events (AEs) will be coded by System Organ Class (SOC) and Preferred Term (PT) using the Medical Dictionary for Regulatory Activities (MedDRA) dictionary. The verbatim term will be included in the AE listings. Adverse event summaries will exclude preferred terms that describe asymptomatic serum ferritin, TSAT, and reticulocyte values (or changes). This approach is justified by the reporting of these values in efficacy summaries and is consistent with the protocol-defined reporting standards for hemoglobin/hematocrit and low iron indices. For the purposes of this study, non-serious anemia (hemoglobin or hematocrit below the normal range or worsened from baseline) or iron deficiency (iron indices below the normal range or worsened from baseline) will not be considered adverse events. Anemia or iron deficiency will be considered end points if an intervention is required.

A treatment-emergent adverse event (TEAE) is defined as an event with onset date on or after the study drug start date. Partial date TEAE classification rules refer to Section 2.3.4. Only TEAEs will be included in summary tables by treatment group.

The incidence of TEAEs will be summarized as the number (percentage) of subjects with TEAEs within SOC and PT by treatment group. Subjects who report the same PT on multiple occasions will be counted once for the PT: under the highest severity (severe > moderate > mild) CTCAE when summarized by severity and under the closest relationship (probably related > possibly related > unlikely related > none) to study drug when summarized by relationship. If a subject reports multiple PT for a SOC, the subject will be counted only once for that SOC. Events with unknown severity or relationship will be counted as unknown.

TEAEs will be summarized as below.

- An overview table, including number of subjects with
  - TEAEs
  - serious TEAEs
  - study drug related TEAEs
  - study drug related Serious TEAEs

- TEAEs by severity
- TEAEs leading to study drug discontinuation or withdrawal from study
- TEAEs leading to death
- TEAE by SOC
- TEAE by PT
- TEAE by SOC and PT
- TEAE by SOC, PT, and Severity(CTCAE)
- Study drug related TEAEs by SOC, PT
- Serious TEAEs by SOC and PT
- Study drug related serious TEAEs by SOC and PT
- TEAEs leading to study drug discontinuation or withdrawal from study by SOC and PT
- TEAEs leading to death by SOP and PT

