### 7.2.1 Adverse Events of Special Interest

Adverse events of special interest include hypophosphatemia, hypersensitivity/anaphylactoid reactions, injection/infusion site reactions, and cardiovascular events. The search strategy will be identified as follows:

- TEAEs of hypophosphatemia:
  - MedDRA PT Blood phosphorus decrease
  - MedDRA PT Blood phosphorus abnormal
  - MedDRA PT Hypophosphataemia
  - MedDRA PT Hypophosphataemic rickets
  - MedDRA PT Rickets familial hypophosphataemic
- TEAEs indicative of hypersensitivity/anaphylactoid reactions:
  - SMQ Anaphylactic reaction
  - SMQ Angioedema
  - PT Hypersensitivity
- TEAEs of injection/infusion site reactions:
  - MedDRA HLT Infusion site reactions
  - MedDRA HLT Injection site reactions
  - MedDRA HLT Administration site reactions NEC
  - MedDRA PT Infusion related reaction

- Cardiovascular TEAEs:
  - Cardiovascular disorders SOC
  - Vascular disorders SOC

The AEs of special interest will be summarized as below:

- Treatment-emergent AESI by SOC and PT
- Serious treatment-emergent AESI by SOC, PT
- Serious or severe treatment-emergent AESI by SOC and PT

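### FCM participants have 8 scheduled blood pressure and heart rate readings after first dosing and oral-iron participants 4, so unequal detection can raise the FCM count of cardiovascular TEAEs, and the SAP does not separate events arising during infusion-visit monitoring

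*SAP*

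**What the plan says.** **Readings.** Protocol 5.3 ties the extra readings to the infusion. Under the words "When administering FCM, the following precautions will be taken" it requires: "Heart rate and blood pressure will be assessed pre-, immediately (within 5 minutes) post, and 30 minutes post administration". Protocol 6.3.1 lists under Group A for Day 0: "Post-administration evaluation to include measurement of sitting heart rate and blood pressure immediately (within 5 minutes) after and 30 minutes after FCM administration". Protocol 6.3.2 repeats the two post-dose readings for Group A on Day 7 and also lists "Pre-administration evaluation to include measurement of heart rate, blood pressure, and body temperature". The synopsis states that Group A "will receive 2 doses (Day 0 and Day 7) of FCM". For Group B the protocol gives vital signs at each visit and no reading after the first oral dose, although that dose is taken in clinic. SAP 7.4.1 describes the same scheme as "On study drug dosing days BP and heart rate will be collected pre-dosing, immediately (within 5 minutes) post, and 30 minutes post dosing" and names no arm. Its planned summary of change in vital signs covers the FCM group only, pre- to post-infusion.

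**Events.** SAP 7.2 says: "Only TEAEs will be included in summary tables by treatment group". SAP 7.2.1 makes cardiovascular events a special-interest category, identified by system organ class. Its listed outputs begin with "Treatment-emergent AESI by SOC and PT", and none is split by time of onset. Protocol 8.5.3 had promised summaries of time to onset and time to recovery for these events. Neither appears in SAP 7.2.1, and SAP section 9 does not list their omission as a change.

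**The concern.** An asymptomatic rise or fall in blood pressure, or a fast heart rate, comes to notice only if someone measures it. FCM participants are measured more often, and the additional measurements fall in the period when staff are watching for reactions. The trial is open-label, so staff know which arm they are observing.

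The primary objective covers safety compared with oral iron, and cardiovascular events are among the few categories singled out. With about 36 participants per arm, one or two events can change how that comparison reads. If more cardiovascular TEAEs appear under FCM, the planned tables do not show whether the difference sits around the infusions, where both a real drug effect and closer monitoring operate, or is spread over the rest of follow-up, where the arms are observed alike.

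The SAP sentence is also a poor description of the data. The protocol defines study drug as either product, and the schedule of events marks oral iron dosing on Days 0, 7, 14 and 28. Read literally, SAP 7.4.1 promises post-dose readings in the oral arm that the protocol does not schedule.

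**Working it through.** The documents state no reading count per arm and no cardiovascular event rate, so there is no figure of the plan's own to reproduce.

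**Step 1. Count scheduled readings after first dosing** (protocol 5.3, 6.3.1 to 6.3.4 and the schedule of events). The Day 0 reading common to both arms precedes dosing and is not counted. The Day 7 visit reading and the Group A pre-administration reading are taken as one.

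| Visit | FCM | Oral iron |
|---|---|---|
| Day 0, after dosing | 2 | 0 |
| Day 7 | 1 pre-dose + 2 post | 1 |
| Day 14 | 1 | 1 |
| Day 28 | 1 | 1 |
| Day 35 | 1 | 1 |
| Total | 8 | 4 |

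The excess is 8 − 4 = 4, exactly the post-infusion readings (2 doses × 2). If the two Day 7 pre-dose entries are separate readings, the count is 9 v 4. If the SAP sentence were also applied to the supervised Day 0 oral dose, it would be 8 v 6.

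**Step 2. Illustrate the effect on detection.** Let p be the chance that one reading is abnormal, equal in both arms with no drug effect. The documents give no value, so p is assumed over a range.

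- Independent readings: P(any abnormal) = 1 − (1 − p)^k, with k = 8 for FCM and k = 4 for oral iron.
- Readings within a visit fully correlated: each visit day counts once. FCM then has 5 visit days (Days 0, 7, 14, 28, 35) and oral iron 4, so k = 5 v 4.

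| p | Independent, 8 v 4 | Fully correlated within visit, 5 v 4 |
|---|---|---|
| 2% | 14.9% v 7.8% | 9.6% v 7.8% |
| 5% | 33.7% v 18.5% | 22.6% v 18.5% |
| 10% | 57.0% v 34.4% | 41.0% v 34.4% |

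At p = 5%, 1 − 0.95^8 = 0.337, 1 − 0.95^5 = 0.226 and 1 − 0.95^4 = 0.185. The ratio is 0.337/0.185 = 1.8 with independence and 0.226/0.185 = 1.2 with full within-visit correlation.

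**Step 3. Restrict to shared readings.** Day 7 pre-dose and Days 14, 28 and 35 give 4 v 4, a ratio of 1.00 for any p.

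**Step 4. Ask whether a reading can become a counted event.** Protocol 7.2 has staff record as an adverse event anything they observe, so the route is open. Protocol 7.1 gives a clinical-significance rule for laboratory values; neither document gives one for vital signs. Protocol 3.2 reports hypertension as a drug-related TEAE in one participant of the earlier 15 mg/kg cohort, so blood pressure events do get recorded in this programme. None of this gives the proportion of abnormal readings that would be recorded as adverse events and coded to a cardiac or vascular class.

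**The case against.** The strongest reply is that the table counts reported adverse events, not readings. An extra abnormal reading adds to the FCM count only if someone judges it an event, records it, and it is coded to a cardiac or vascular class. A reader might infer from 8 v 4 that detection alone inflates the FCM count. The documents do not support that: they leave the route open but do not show that it operates, and a real infusion effect would appear in the same four readings. This objection stands, and it limits the point to what can happen.

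Second, the percentages above describe a by-arm count of any abnormal reading, which the SAP does not plan. A reader might take them for expected TEAE rates; they are not. Independence is also the extreme case, since readings minutes apart in one child are clustered.

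Third, some information is already there. Post-infusion vital signs are summarized for FCM separately, adverse events are listed, onset time is recorded, and hypersensitivity and infusion-site reactions have their own categories. That helps a reader who works through listings, but it does not put the split in the by-arm table.

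Fourth, a reader might infer that the cure is to compare arms only on events outside the infusion window. That would remove real infusion reactions, including symptomatic ones that need no measurement to surface, while oral-arm events after the supervised first dose stayed in. It would favour FCM and should not be done.

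**Conclusion.** The point holds as a possibility that the planned tables cannot examine. The count of 8 v 4 scheduled readings follows from the protocol, assuming each participant receives both infusions and attends every visit. Cardiovascular TEAEs are tabulated by arm, and the SAP separates nothing by onset.

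The size of any excess in TEAEs cannot be derived from the documents. At an assumed 5% per reading, the illustrative ratio for any abnormal reading lies between about 1.2 and 1.8, depending on within-visit correlation. A higher FCM count would not by itself show artefact, and the documents do not establish that a distorted result will occur. The change is worth making because it is cheap, drops nothing and uses data already recorded.

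**What to change.** **SAP 7.2.1.** Keep the all-events row of cardiovascular TEAEs by arm as the main comparison. Beneath it add two supportive rows: onset from infusion start to the last post-infusion reading, 30 minutes after the infusion ends; and all other onset times. State that the second row alone is not to be used to compare the arms, because real infusion effects fall in the first. Restore the time-to-onset summary for events of special interest promised in protocol 8.5.3.

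**SAP 7.4.1.** State that post-dose readings exist for FCM only, in line with protocol 5.3 and 6.3. If markedly abnormal blood pressure or heart rate is tabulated by arm, use the shared readings (Day 7 pre-dose, Days 14, 28 and 35) and show the post-infusion readings for FCM only.

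**Cost.** SAP wording and a few extra table rows. Onset time (protocol 7.2) and infusion start and stop times (protocol 6.3.1 and 6.3.2) are already collected. Counts in the split rows will be sparse at about 36 per arm, so they should be read descriptively.
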